## 6.6 TOXICITY MANAGEMENT

Guidelines for toxicity management associated or possibly associated with SUPLEXA are located in the appendices for:

- CRS toxicity (Appendix 6, Section 10.7)
- TLS toxicity (Appendix 7, Section 10.8)

## 6.7 TREATMENT OF OVERDOSE

Any overdose of study intervention is unlikely given the premade doses, but should they occur must be recorded in the eCRF including quantity of the excess dose and the duration of the overdose. AEs associated with an overdose or incorrect administration of study intervention should be recorded in the AE eCRF. An overdose will not be considered an SAE unless the outcome of the overdose meets seriousness criteria.

For this study, any dose of study intervention greater than the number of cells in a given infusion bag will be considered an overdose as will any administration greater than specified in a particular dose reduction cohort.

In the event of overdose, the subject should be observed closely for signs of toxicity. Appropriate supportive treatment should be provided if clinically indicated.

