- **Subsequent weekly infusions (after dose 3 with SUPLEXA batch 1 and batch 2)**

After completion of the first 3 weekly SUPLEXA batch 1 infusions, based on emerging data from prior subjects, disease evaluation (as described below), the discretion of the Investigator, and in agreement with the subject, treating physician and the Sponsor's Medical Monitor (or designee), the treatment period of SUPLEXA may be extended as follows:

Subjects will continue to receive SUPLEXA treatments of approximately 5 B cells, every 2 weeks with a wider window -1 day to +7 days until either, a) depletion of SUPLEXA batch 1 doses \*, or b) disease progression is assessed by the Investigator per iRECIST v1.1, or c) unacceptable toxicity, or other reasons for discontinuation as described in Section [7.2](#).

The 5 B cells will be provided as two bags of SUPLEXA targeted at 2.5B cells until all product used, unless there is only a single dose unit left, upon which time the subject may receive a single bag until more SUPLEXA is manufactured for them.

An additional SUPLEXA batch #2 may be manufactured for a subject based on (a) last dose of batch 1 and the investigator and subject and sponsor agree, then prior to the administration of the last SUPLEXA dose, blood can be drawn for SUPLEXA manufacturing of batch 2; or (b) > 2 weeks and < 8 weeks after the last dose of SUPLEXA administered, blood is collected for batch 2.

Note that subjects enroled in SUPLEXA-101, Version 3.0 or 2.0, and had SUPLEXA manufacturing started on or before October 31, 2022, may logistically be unable to have the consecutive administration of the recommended dosing regimen. These patients are therefore exempt from the defined gap in dosing, and the sequential dosing regimen described above. However, upon possible restarting additional doses of SUPLEXA, the dosing must be sequential until either, a) depletion of SUPLEXA batch 1 doses \*, or b) disease progression is assessed by

the Investigator per iRECIST v1.1, or c) unacceptable toxicity, or other reasons for discontinuation as described in Section 7.2.

Subjects will be monitored at the clinic for at least 90 minutes (+/- 30 min) after each infusion for AE and ISR.

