##### **4.1.2.2 Subsequent Weekly Infusions (SUPLEXA Batch 1 and Batch 2)**

After completion of the first 3 weekly SUPLEXA batch 1 infusions, based on emerging data from prior subjects, disease evaluation (as described below), the discretion of the Investigator, and in agreement with the subject, treating physician and the Sponsor's Medical Monitor (or designee), the treatment period of SUPLEXA may be extended as follows:

Subjects will continue to receive SUPLEXA treatments of approximately 5 B cells, every 2 weeks with a wider window -1 day to +7 days until either, a) depletion of SUPLEXA batch 1 doses \*, or b) disease progression is assessed by the Investigator per iRECIST v1.1, or c) unacceptable toxicity, or other reasons for discontinuation as described in Section 7.2.

The 5 B cells will be provided as two bags of SUPLEXA targeted at 2.5B cells until all product used, unless there is only a single dose unit left, upon which time the subject may receive a single bag until more SUPLEXA is manufactured for them.

An additional SUPLEXA batch #2 may be manufactured for a subject based on (a) last dose of batch 1 and the investigator and subject and sponsor agree, then prior to the administration of the last SUPLEXA dose, blood can be drawn for SUPLEXA manufacturing of batch 2; or (b) > 2 weeks and < 8 weeks after the last dose of SUPLEXA administered, blood is collected for batch 2.

Note that subjects enroled in SUPLEXA-101, Version 3.0 or 2.0, and had SUPLEXA manufacturing started on or before October 31, 2022, may logistically be unable to have the consecutive administration of the recommended dosing regimen. These patients are therefore exempt from the defined gap in dosing, and the sequential dosing regimen described above. However, upon possible restarting additional doses of SUPLEXA, the dosing must be sequential until either, a) depletion of SUPLEXA batch 1 doses \*, or b) disease progression is assessed by the Investigator per iRECIST v1.1, or c) unacceptable toxicity, or other reasons for discontinuation as described in Section 7.2.

Subjects will be monitored at the clinic for at least 90 minutes (+/- 30 min) after each infusion for AE and ISR.

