#### Events Meeting the AE Definition

- Any abnormal laboratory test results (hematology, clinical chemistry, or urinalysis) or other safety assessments (e.g., ECG, radiological scans, vital signs measurements), including those that worsen from baseline, considered clinically significant in the medical and scientific judgment of the Investigator (i.e., not related to progression of underlying disease).
- Exacerbation of a chronic or intermittent pre-existing condition including either an increase in frequency and/or intensity of the condition.
- New conditions detected or diagnosed after study intervention administration even though it may have been present before the start of the study.
- Signs, symptoms, or the clinical sequelae of a suspected drug-drug interaction.
- Signs, symptoms, or the clinical sequelae of a suspected overdose of either study intervention or a concomitant medication. Overdose per se will not be reported as an AE/SAE unless it is an intentional overdose taken with possible suicidal/self-harming intent. Such overdoses should be reported regardless of sequelae.
- “Lack of efficacy” or “failure of expected pharmacological action” per se will not be reported as an AE or SAE. Such instances will be captured in the efficacy assessments. However, the signs, symptoms, and/or clinical sequelae resulting from lack of efficacy will be reported as AE or SAE if they fulfil the definition of an AE or SAE.

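### Section 6.7 makes every planned two-bag dose an overdose, and the sections disagree on the extension interval and the per-dose cell range

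*Combined protocol and SAP*

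**What the plan says.** **Overdose.** Section 6.7 defines it in two limbs. The first is that "any dose of study intervention greater than the number of cells in a given infusion bag will be considered an overdose". The second limb sets a further limit by cohort: "as will any administration greater than specified in a particular dose reduction cohort". An overdose "must be recorded in the eCRF including quantity of the excess dose and the duration of the overdose", and the subject is to be watched closely. On reporting, 6.7 adds: "An overdose will not be considered an SAE unless the outcome of the overdose meets seriousness criteria". Section 10.3.1 agrees: "Overdose per se will not be reported as an AE/SAE unless it is an intentional overdose", an exception it ties to possible self-harm.

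**Planned dose.** The first three doses are single bags with a target of 2.5 billion cells. After that, Section 1.1 plans "treatments of approximately 5 B cells, every 2 weeks". Section 4.1.2.2 repeats this and adds: "The 5 B cells will be provided as two bags of SUPLEXA targeted at 2.5B cells". It allows one departure from two bags: "unless there is only a single dose unit left, upon which time the subject may receive a single bag". Note r of the Schedule of Activities (1.3) and Section 4.3 also give 5 billion cells every 2 weeks, and 6.1 gives an infusion time for two-bag doses.

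**Interval.** The administration instructions in 6.1 say weekly after dose 3, with a window of -1 to +7 days. The text of 1.1 and 4.1.2.2 says every 2 weeks with the same window, although the headings above that text still say weekly.

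**Cell range at the 2.5 billion target.** Sections 1.1 and 4.1.2 give 1.9-3.1 billion, 4.3 gives 1.9-3.9 billion, and 6.1 gives 1.3-3.1 billion. No range is given for the two-bag dose.

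**Supply and duration.** Batch 1 may yield up to 15 units (1.1, 4.1.2.2). Section 1.1 puts treatment with two 15-unit batches at up to 24 weeks. Dosing may pause for up to 60 days while batch 2 is made.

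**The concern.** The overdose limit is one bag and the planned extension dose is two, and 6.7 makes no exception for this. Its second limb refers to a dose-reduction cohort that the protocol does not define: 4.1 names only the solid tumour and haematologic cohorts, and the DLT rules in 6.5.1 delay or stop infusions without creating another.

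A site that follows 6.7 would log routine doses as overdoses, each with an excess quantity and a duration. A real overdose would sit among them until someone separated the two. The interval and range conflicts give sites two incompatible rules for when an extension dose is on schedule and for which cell counts are acceptable.

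The stakes are limited. Overdose is not an endpoint (3) or a stopping trigger (7.1, 7.2), and it is not in itself an AE or SAE outside the intentional case. The two DLT periods follow doses 1 and 2, which are single bags (6.5, 6.5.1), and the dose actually given is recorded (6.4).

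**Working it through.** **1. The plan's own figures.** Two bags x 2.5 = 5.0 billion cells, as 4.1.2.2 states. Apply the 4.1.2.2 rule (two bags per dose, or one if only one is left) to two batches of 15:

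- Batch 1: 15 - 3 single bags = 12 bags, or 6 two-bag doses.
- Batch 2: 15 bags = 7 two-bag doses + 1 single-bag dose.
- Extension doses: 6 + 8 = 14, which matches the maximum of 14 in 4.3.

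**2. Overdose test.** The 5.0 billion target exceeds the highest single-bag limit printed anywhere (3.1 or 3.9 billion). Whatever the yield, two bags hold more than one, so every two-bag dose meets the literal definition. Single-bag doses do not.

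| Assumed yield | Doses | Two-bag doses (literal overdoses) |
|---|---|---|
| No extension | 3 | 0 |
| One batch of 5 bags | 3 + 1 = 4 | 1 |
| One batch of 10 | 3 + 3 + 1 = 7 | 3 |
| One batch of 15 | 3 + 6 = 9 | 6 |
| Two batches of 10 | 7 + 5 = 12 | 3 + 5 = 8 |
| Two batches of 15 | 3 + 14 = 17 | 6 + 7 = 13 |

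Only the 15-unit maximum comes from the protocol; the 5- and 10-bag yields are assumptions that show the range.

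**3. Interval.** With a window of -1/+7 days, weekly allows days 6-14 after the previous dose and two-weekly allows days 13-21. Only days 13 and 14 satisfy both. A dose on day 7 complies with 6.1 and departs from 4.1.2.2; a dose on day 18 does the reverse.

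**4. Range.** The lower bound is 1.3 or 1.9 billion and the upper bound 3.1 or 3.9 billion. If a two-bag dose simply doubles the bag range (an assumption), the implied ranges are 3.8-6.2, 3.8-7.8 or 2.6-6.2 billion.

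**5. Duration with two 15-unit batches.** Doses 1-3 fall at weeks 0, 1 and 2.

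- Two-weekly, no gap: 2 + 14 x 2 = week 30.
- Two-weekly, 60-day gap: batch 1 ends at week 14; 14 + 60/7 + 7 x 2 = week 36.6.
- Two-weekly, shortest windows: 5 + 5 + 14 x 13 = 192 days = week 27.4. If doses 1-3 are kept at least 1 week apart, as 6.5.1 says: 7 + 7 + 182 = 196 days = week 28.0.
- Two bags weekly, as 6.1 can be read: 2 + 14 = week 16; with the gap, 56 + 60 + 49 = 165 days = week 23.6.

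Of these, only the weekly schedules end within 24 weeks. On the nominal two-weekly schedule with equal batches, the last dose falls within 24 weeks up to 12 bags per batch without a gap (week 24.0). With the 60-day gap the limit is 8 bags (week 22.6); 9 bags gives week 24.6.

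**6. Worked example for 15 units.** Three weekly doses, three two-weekly doses and one final dose use 3 + 3 x 2 + 1 = 10 bags, or 11 if the last dose is two bags. That leaves 5 or 4 of the 15 unassigned. The unit is printed as 2.5M in both 1.1 and 4.1.2.2, where every other dose is in billions.

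**The case against.** The strongest defence is that 6.7 was never meant to catch two-bag doses. It calls overdose unlikely because doses are premade, which would make no sense if routine doses counted, and its wording could be read bag by bag. Section 6.1 plainly tells sites to give two bags, so a site may never log one as an overdose. This is fair evidence of intent, but it does not rescue the text. A bag cannot deliver more cells than it holds, so on the per-bag reading that limb catches nothing.

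Several limits do stand:

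- The 1.9-3.9 billion range appears only in the dose justification. Between the operative sections, the range conflict is the lower bound, 1.3 against 1.9 billion.
- The weekly interval is an instruction only in 6.1; the two headings instruct nothing, and four other places say every 2 weeks. But 6.1 is the section that tells sites how to administer the product.
- The 13 of 17 ceiling needs two optimal batches and no early stop, and the 24-week figure is a hedged forecast that 4.4 does not repeat.
- The pharmacy manual, the Investigator's Brochure and the eCRF are not available here and may soften the practical effect.
- The main conflicts are of consistency rather than calculation.

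**Conclusion.** The concern holds. On the current text, every two-bag extension dose is both planned and an overdose, and the interval and per-dose range differ between sections that give instructions. The size runs from 0 of 3 doses (no extension) to 13 of 17 (two 15-bag batches), with 6 of 9 for one full batch. These counts assume the bag rule in 4.1.2.2 and the yields shown.

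The duration and unit-count mismatches are secondary. On the two-weekly plan, two full batches end at week 30, or 36.6 with the gap, against a stated 24. Even the shortest windows give 27.4 or 28.0, so the conclusion does not depend on that choice.

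The demonstrated consequence is unreliable overdose records and conflicting instructions to sites. No bias in the DLT or AE endpoints is shown. This should be fixed, but it does not threaten the primary analysis.

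**What to change.** The sponsor should reconcile Sections 1.1, 1.3, 4.1.2, 4.3, 6.1 and 6.7 so that dose, unit, cell range, interval and overdose definition agree, and no dose is both planned and an overdose. It should also:

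- define or remove the dose-reduction cohort in 6.7;
- state whether a cell range applies to the two-bag dose;
- bring the extension headings in 1.1 and 4.1.2.2 into line with the reconciled interval;
- restate the 15-unit example and the treatment duration from the reconciled regimen.

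Which dose, interval, range or overdose rule is right is for the sponsor to decide; none is proposed here.

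The cost is protocol amendment wording and recalculated forecast figures. The stated treatment duration may change.

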## 6.8 CONCOMITANT GENERIC THERAPY

Any medication or vaccine (including over the counter or prescription medicines, vitamins, and/or herbal supplements) that the subject is receiving within 4 weeks before the first dose of study intervention through 24 weeks after the last dose of study intervention must be recorded along with:

- Name of medication/therapy (generic name)
- Reason for use
- Dates of administration including start and end dates
- Dosage information including dose and frequency

Concomitant medications administered 24 weeks after the last dose of study intervention should be recorded for SAEs.

Concomitant medications necessary for the health and well-being of the subject and that do not interfere with study assessments are permitted during the study at the Investigator's discretion. All treatments that the Investigator considers necessary for a subject's welfare may be administered at the discretion of the Investigator in keeping with the community standards of medical care. This includes the use of appropriate medications for the treatment of AEs and/or concurrent illnesses under the direction of the Investigator. All medications must be recorded in the source and on the appropriate eCRFs. Start of new medications of any type (over the counter or prescription) during the study however is strongly discouraged as it can be deemed confounding.

Concurrent use anti-androgen therapies subjects with prostate cancer and anti-estrogen therapies for subjects with breast cancer is allowed. Bisphosphonate IV (i.e., zoledronic acid) or denosumab subcutaneous (SC) therapy must be initiated prior or within the first 60 days of the first administration of the study intervention. Oral bisphosphonate may be initiated at any point in the study for the treatment of osteoporosis.

Concurrent use of continued targeted therapies and immune checkpoint inhibitor therapies (e.g., anti-PD-1, anti-PD-L1 or anti-CTLA4) may be allowed provided the subject was on a stable dose for at least 3 months prior to enrolment and had at least a stable disease response.

Concurrent use of dexamethasone (up to 4 mg/day) may be allowed provided the subject was on a stable dose for at least 30 days.

The Sponsor's Medical Monitor should be contacted if there are any questions regarding concomitant or prior therapy.

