## 1 PROTOCOL SUMMARY

### 1.1 SYNOPSIS

**Protocol Title:** A Phase 1, First-in-Human, Open-label Single Agent Study of SUPLEXA Therapeutic Cells in Patients with Metastatic Solid Tumours and Haematologic Malignancies

**Short Title:** Phase 1 Study of SUPLEXA in Patients with Metastatic Solid Tumours and Haematologic Malignancies

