### **Number of Subjects**

Up to 60 subjects may be enroled with a cap of about 8 subjects per individual tumour type with a prioritization and focus on melanoma, breast, prostate, lung, and haematological malignancies. If promising anti-tumour activity coupled with acceptable safety is observed, overall sample size and/or cap per tumour type may be expanded.

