#### Type of Subject and Disease Characteristics

##### Solid Tumours

2. Histologically or cytologically confirmed diagnosis of locally advanced or metastatic solid tumour.
3. Have 1 or more tumours measurable based on RECIST v1.1 as assessed by the local site Investigator. Radiographic scans should be obtained within 5 weeks of Screening. Lesions situated in a previously irradiated area are considered measurable if objective progression has been demonstrated following radiation to such lesions.
4. Subjects who did not attain a durable response after receiving at least one standard/approved therapies which may include chemotherapy, targeted agents, radio-, immuno- conjugates, check point inhibitors or where there is no approved therapy. This includes subjects who attained a long-term stable disease (SD), or partial response (PR) are eligible. Long term SD subjects on a checkpoint inhibitor may continue checkpoint inhibitor (CPI) therapy.  
\* Any therapies defined as immunosuppressive require a washout period of at least 4 weeks, defined as 4 weeks (28 days) prior to blood collection for SUPLEXA manufacturing and any SUPLEXA dose administration.

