## 9 STATISTICAL CONSIDERATION

### 9.1 SAMPLE SIZE DETERMINATION

Approximately 60 subjects will be enroled with a cap of about 8 subjects per individual tumour type (e.g., melanoma, breast, prostate, lung, haematological malignancies, etc.). If promising anti-tumour activity coupled with acceptable safety is observed, overall sample size and/or cap per tumour type may be expanded.

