### 9.3.2 Efficacy Analysis

#### Solid Tumour Cohort

The secondary endpoint of ORR will be defined as the proportion of subjects with BOCR of either a CR or PR as assessed by the Investigator using RECIST v1.1 in the Response Evaluable Population as both unconfirmed or confirmed status. ORR will be reported as a proportion along with the corresponding 2-sided 95% Clopper-Pearson exact CI.

A sensitivity analysis of the primary endpoint will be performed in the Response Evaluable Population.

Other secondary and exploratory endpoints are defined as follows for the whole cohort or analysed by tumour type:

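### The trial is called single agent but permits continued checkpoint inhibitor, targeted or hormonal therapy; Section 9.3.2 plans no split by it, so pooled CBR, TTP and PFS cannot isolate SUPLEXA

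*Combined protocol and SAP*

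**What the plan says.** The title reads "A Phase 1, First-in-Human, Open-label Single Agent Study of SUPLEXA Therapeutic Cells", and Sections 2.1 and 4.2 call the treatment monotherapy. There is one arm and no comparator.

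Three classes of active anti-cancer drug may nevertheless run alongside SUPLEXA:

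- **Checkpoint inhibitors.** Inclusion criterion 4 in Section 5.1 states "Long term SD subjects on a checkpoint inhibitor may continue checkpoint inhibitor (CPI) therapy".
- **Checkpoint inhibitors and targeted therapies.** Section 6.8 allows "Concurrent use of continued targeted therapies and immune checkpoint inhibitor therapies" if the subject was "on a stable dose for at least 3 months prior to enrolment and had at least a stable disease response".
- **Hormonal therapy.** Section 6.8 allows anti-androgens in prostate cancer and anti-oestrogens in breast cancer, and attaches no condition on dose stability or disease status.

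The prohibition of anti-cancer therapy in Section 6.8.2 exempts what the protocol itself specifies, so it does not remove these subjects.

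On analysis, the Response Evaluable Population in Section 9.2 neither excludes nor separates them. Section 9.3.2 gives ORR in that population and continues: "Other secondary and exploratory endpoints are defined as follows for the whole cohort or analysed by tumour type". It also names an Efficacy Evaluable Population for the main analyses, but Section 9.2 does not define one, so it cannot be relied on to make the separation. Section 9 contains no stratum, sensitivity analysis or censoring rule for concurrent anti-cancer therapy.

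**The concern.** Subjects on a continued checkpoint inhibitor or targeted drug are selected because that drug is already holding their disease. Section 9.3.2 counts stable disease at 6 months as clinical benefit, and runs TTP and PFS from the first SUPLEXA dose. Time controlled by the continued drug therefore enters all three summaries as if SUPLEXA had produced it. Without a comparator, nothing in the pooled figure separates the two sources. If outcomes are better on background therapy than off it, the bias favours SUPLEXA.

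The figures have a use. Sections 1.1 and 9.1 allow the overall sample size or the tumour-type cap to be enlarged if anti-tumour activity looks promising and safety is acceptable. The synopsis sets enrolment "with a prioritization and focus on melanoma, breast, prostate, lung, and haematological malignancies", which includes the two tumour types for which hormonal therapy is expressly allowed.

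**Working it through.** **What can be reproduced.** Section 9.1 says "Approximately 60 subjects will be enroled with a cap of about 8 subjects per individual tumour type". It states no hypothesis, null or target rate, alpha or power, so the 60 cannot be re-derived. The point concerns attribution and disputes no stated figure.

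**Inputs for the illustration.** All are assumptions, because the documents give none of them:

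- *f*: share of subjects on background therapy, 10–50%
- *b*: 6-month clinical benefit on background therapy alone, 40–80%
- *m*: 6-month clinical benefit off it, 10–20%
- SUPLEXA effect: zero

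**Clinical benefit rate.** Pooled rate = f·b + (1 − f)·m, and the excess over *m* is f·(b − m).

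| m | b | f = 10% | f = 25% | f = 50% |
|---|---|---|---|---|
| 10% | 40% | 13.0% | 17.5% | 25.0% |
| 10% | 60% | 15.0% | 22.5% | 35.0% |
| 10% | 80% | 17.0% | 27.5% | 45.0% |
| 20% | 40% | 22.0% | 25.0% | 30.0% |
| 20% | 60% | 24.0% | 30.0% | 40.0% |
| 20% | 80% | 26.0% | 35.0% | 50.0% |

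The pooled rate runs from 13% to 50%. The smallest excess is 0.10 × (0.40 − 0.20) = 2 percentage points; the largest is 0.50 × (0.80 − 0.10) = 35 points. Under the same assumptions, subjects off background therapy would show 10–20%.

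**Time to progression.** Assume exponential times with a median of 3 months off and 9 months on background therapy. The pooled median *t* solves f·exp(−t·ln2/9) + (1 − f)·exp(−t·ln2/3) = 0.5. This gives 3.28, 3.78 and 4.96 months at f = 10%, 25% and 50%, against 3 months off background therapy. PFS is exposed in the same way, since it also starts at the first dose and counts progression.

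**Objective response.** Appendix 5 requires a fall of at least 30% from the on-study baseline for a partial response, so shrinkage achieved before entry does not count. With b = 2–10%, m = 0–2% and f = 25%, pooled ORR is 0.25 × 0.02 + 0.75 × 0 = 0.5% at the low end and 0.25 × 0.10 + 0.75 × 0.02 = 4.0% at the high end. The excess f·(b − m) is at most 0.25 × 0.10 = 2.5 points. That reasoning does not protect hormonal therapy, for which no prior stability is required.

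**Tumour-type groups.** The tumour-type analysis does not cure this, because background therapy can vary within a type or cluster in one. In a group of 8, the probability of at least 4 subjects with clinical benefit is 0.005 at a true 10% and 0.056 at 20%. It is 0.826 if all 8 are on background therapy with b = 60%.

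**The case against.** The case for leaving the plan alone has real parts.

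- **The endpoints are not primary.** The primary objective is safety, efficacy is called preliminary, and there is no efficacy threshold. CBR and PFS are exploratory; TTP and ORR are secondary. This limits the consequence, but a descriptive estimate still has to describe the stated treatment.
- **A separate SAP is promised.** Section 9.3 calls itself a summary and says the SAP will prevail. A reader might infer that the sponsor will never split by concurrent therapy. The documents do not support that: they show only that Section 9.3.2 does not specify it. Individual listings are planned and concomitant drugs are recorded, so subjects could be traced. Traceability is still not a prespecified estimate.
- **ORR.** A reader might infer that ORR is inflated as CBR is. For stable checkpoint or targeted subjects the on-study baseline largely prevents this.
- **Entry status.** A reader might infer that everyone on background therapy enters with controlled disease. The condition of at least stable disease applies only to checkpoint and targeted therapy; nothing says it of hormonal subjects. Section 6.8 also discourages starting new medication as potentially confounding, though it does not forbid it.
- **The split is not a clean cure.** Inclusion criterion 4 admits subjects with long-term stable disease or partial response generally, so the group without concurrent therapy may also contain subjects controlled by earlier treatment. This stands, and the fix has to say so.

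**Conclusion.** The point holds for what Section 9.3.2 specifies. As written, pooled CBR, TTP and PFS do not answer the single-agent question, and ORR is a lesser concern that rests mainly on hormonal therapy.

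The size is unknown. Under the assumed inputs and no SUPLEXA effect, pooled CBR is 13–50% against 10–20% off background therapy, an excess of 2 to 35 points. These are illustrations of what is possible. A reader might take them as an estimate of bias in this trial, but the documents give neither the share on background therapy nor any rate, so they cannot support that. The direction rests on outcomes being better on background therapy than off it. That is plausible for subjects selected for disease control, but it too is an assumption.

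**What to change.** In Section 9.3.2, and in the SAP when written:

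1. Prespecify ORR, CBR, TTP and PFS in subjects with no concurrent anti-cancer therapy as the main single-agent estimate.
2. Show subjects on continued checkpoint inhibitor, targeted or hormonal therapy separately, with the drug class identified.
3. Give the pooled figure only beside these two.
4. State that the no-concurrent-therapy group may still include subjects who entered with long-term stable disease or partial response from prior therapy, and report disease status at entry alongside.
5. Make the split at cohort level. Within tumour types capped at about 8 the strata would be very small, so use subject listings there.

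No eligibility or treatment rule changes. Section 6.8 already requires drug name, reason, dates and dose to be recorded. Since the study is open-label and Section 2.3.1 reports more than 15 subjects enrolled by 19 September 2022, the split should be fixed before more outcomes accumulate.

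The cost is a smaller denominator and a wider interval. Interval width scales roughly with 1/√n, so removing a share *f* widens it by a factor of about 1/√(1 − f): 1.05 at 10%, 1.15 at 25% and 1.41 at 50%. For scale, 15 of 60 has an exact 95% interval of 14.7–37.9%, and 4 of 8 has 15.7–84.3%. The wider interval reflects the single-agent information the trial actually holds.
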